## **3.2 Analysis Populations**

The following populations will be analyzed:

**Modified Intent-to-treat (mITT) Population:** The primary population for efficacy analyses will be a Modified Intent-to-treat (mITT) Population defined as all subjects who receive at least 1 dose of study medication. The mITT Population will be used for tables of demography, baseline characteristics, and efficacy.

**Responder Population:** The Responder Population is defined as subjects in the mITT population that achieved a PR or CR response at any post-baseline response assessment.

**Non-responder Population:** The Non-responder Population is defined as any subject in the mITT Population who is not a responder.

The responder and non-responder populations will be used for some subgroup analyses.

**Safety Population:** The Safety Population is defined as all subjects who receive at least 1 dose of study medication. In this study, the Safety Population is equivalent to the mITT Population.

### 3.3 Subject Disposition and Evaluability

Subjects who failed screening (i.e., subjects who signed the informed consent were screened but never started the study treatment, and their basic demographics and any AE after signing the informed consent may have been collected in the CRF) will be excluded from any populations defined in [Section 3.2](#). Therefore, these subjects will be excluded from any summary tables or listings.

The number of subjects discontinuing from the study and the primary reason for discontinuation will be summarized.

### 3.4 Protocol Deviations

All protocol deviations will be identified and classified as major or minor before clinical database lock and will be presented in a listing.

**Major Deviation:** Protocol deviation that may impact the accuracy, and/or reliability of the study data or that may impact subject rights, safety or well-being.

**Minor Deviation:** Protocol deviation that does not impact the accuracy, and/or reliability of the study data or subject rights, safety or well-being.

**Serious Non-compliance:** Serious non-compliance presents a significant risk to the safety of study patients or significantly affects the scientific value of the reported results of the study. This classification may include fraud, scientific misconduct and serious breaches of ethical conduct. Persistent clinical investigator site noncompliance, even if not serious, is also considered within this definition.

### **3.5 Demographics and Baseline Characteristics**

#### **3.5.1 Demographics**

Subject demographics and baseline characteristics will be summarized for the mITT Population. Descriptive statistics will be provided for age, height, weight, and body mass index (BMI). Frequencies and percentages will be tabulated for sex, race, and ethnicity.

BMI will be calculated as follows:

$$\text{BMI (kg/m}^2\text{)} = \text{weight (kg)/height}^2\text{ (m}^2\text{)},$$

where the weight and height are obtained at baseline.

#### **3.5.2 Medical History**

Medical history will be summarized by primary System Organ Class (SOC) and Preferred Term (PT). Medical history will be coded using Medical Dictionary for Regulatory Activities (MedDRA) Version 20.1 (or higher) terminology.

#### **3.5.3 cGVHD History**

Transplant history will be summarized for:

- Indication for transplant
- Stem cell type (bone marrow, peripheral blood, cord blood)
- Donor source (related, unrelated)
- Conditioning regimen (myeloablative, nonmyeloablative)
- Donor age
- Donor gender
- Donor-recipient gender mismatch

- Donor-recipient cytomegalovirus (CMV) serostatus

The baseline characteristics of cGVHD will be summarized for:

- Time from most recent transplant to cGVHD diagnosis
- Time from cGVHD diagnosis to study enrollment
- Time from most recent transplant to enrollment
- Prior therapies for cGVHD will be summarized for:
  - Number of lines of prior systemic therapies
  - Prior systemic therapies
- Organ involvement will be summarized for
  - Number of organs involved at baseline
  - Organ involvement at baseline including:
    - NIH Skin Score and Skin Features Score
    - NIH Eye Score
    - NIH-modified Oral Mucosa Rating Scale (OMRS)
    - NIH Esophagus Score
    - NIH Upper Gastrointestinal (GI) Score
    - NIH Lower GI Score
    - Alanine transaminase (ALT), Alkaline phosphatase (ALP), Total Bilirubin
    - NIH Lung Symptom Score and Forced Expiratory Volume in One Second (FEV1) (% predicted)
    - NIH Joint and Fascia Score and P-ROM score
    - Global Severity Rating

### 3.5.4 Other Baseline Characteristics

Other baseline values including Karnofsky Performance Scale ([Appendix E; Karnofsky et al., 1949](#)) and childbearing potential will also be summarized.

## 3.6 Prior and Concomitant Medications

Concomitant medications will be coded using the World Health Organization Drug Dictionary. Prior medications are defined as those medications that began and

stopped before the start of study treatment. Concomitant medications are defined as medications taken after the start of study treatment and during the study period, including those began before but ongoing at the start of study treatment. If a medication start date is partially or fully missing and it is unclear as to whether the medication is prior or concomitant, it will be assumed that the medication is concomitant.

Number and percentage of incidence of prior and CM will be summarized according to Anatomical Therapeutic Class (ATC) and preferred drug name.

### **3.7 Treatment Compliance and Exposure**

The relative dose intensity (RDI) will be used to assess the treatment compliance. The RDI is defined as:

$$\text{RDI (\%)} = 100 \times \text{ADI (mg/day)} / \text{PDI (mg/day)},$$

where ADI and PDI are the actual dose intensity and planned dose intensity, respectively:

$$\text{PDI (mg/day)} = \text{planned cumulative dose (mg)} / \text{duration of exposure (days)},$$

$$\text{ADI (mg/day)} = \text{actual cumulative dose (mg)} / \text{duration of exposure (days)}.$$

The planned cumulative dose is the planned daily dose amount multiplied by the duration of exposure, while the actual cumulative dose is the sum of actual total daily dose amount over the duration of exposure. The actual total daily dose will need the information of dose change and dose held (interruption) captured in CRF (Missed Dose and Dose Modification). If a subject did not take any study drug, the actual RDI by definition is zero.

The duration of exposure is defined as:

$$\text{Duration of exposure (days)} = (\text{Date of last dose} - \text{Date of Study Day 1}) + 1.$$

The descriptive summary statistics of the treatment duration, actual cumulative dose, ADI, and RDI will be presented.

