Blood samples (approximately 5 mL) for determination of plasma concentrations of KD025 and its metabolites, will be collected on Day 1 of Cycles 1 and 2 at the following time points: Pre-dose (Time 0), and 1, 2, 3, 4, 5, and 6 hours after dosing (after first dose for subjects in the BID group). In addition, subjects will have samples collected pre-dose on Day 1 of Cycle 4 and pre-dose at the Cycle 7 Day 1 visit. See [Section 11](#) for additional information.

Blood Sampling for Pharmacodynamics (PD)

All subjects will have PD blood samples drawn up to 4 times over the course of the study: Pre-dose on Cycle 1 Day 1, Cycle 2 Day 1 (4 weeks), Cycle 4 Day 1 (12 weeks) and Cycle 7 Day 1 (24 weeks). Samples will be analyzed to evaluate changes in the expression of several cytokines in plasma (including IL-17A, IL-21, and IL-2), and changes in percentages of circulating Th17 and Treg cells in blood. See [Section 12](#) for additional information.

KD025 Administration and Treatment Duration

Subjects will receive their first dose of study drug in the clinic on Day 1 of Cycle 1, and then study drug will be dispensed for home administration. On scheduled visit days, subjects will take their dose at the clinic.

Subjects will receive KD025 200 mg QD, KD025 200 mg BID, or KD025 400 mg QD. Subjects will be treated until disease progression or unacceptable toxicity. Subjects with a “LOR - Mixed” response assessment may continue treatment with KD025 and remain on study if the investigator considers continued treatment to be in the subject’s best interest only after approval from the medical monitor and documentation of the subject’s willingness to continue.

Subjects who have SD, PR, or CR at the time of decision to discontinue treatment and who come off study for reasons other than AEs will be tapered off of KD025 by lowering the dose by 50% every 2 weeks (see [Section 14.1](#) for additional details) until they reach a dose of 100 mg QD or equivalent. Further instructions will be listed in the pharmacy manual.

Study Drug Diary

Subjects will be given a study drug diary to record the details of each dose of study drug. Diaries will be dispensed/collected on Day 1 of each cycle. Compliance with oral dosing will be confirmed using patient diaries, which will be examined at each visit.

Response and Activity Assessments

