14. STUDY DRUG

14.1. Dose and Schedule of Study Drug

Kadmon will provide each investigator with adequate supplies of KD025.

Eligible subjects will receive KD025 200 mg QD, KD025 200 mg BID, or KD025 400 mg QD.

Study drug will be dispensed by the site pharmacist. After the completion and review of all screening and baseline procedures, qualified subjects will receive study drug.

Cohort	No. of Subjects	Dosage	Number of 100 mg capsules to be administered per dose	Number of 200 mg tablets to be administered per dose
Cohort 1	16 subjects	200 mg KD025 QD	2	1
Cohort 2	16 subjects	200 mg KD025 BID	2	1
Cohort 3	16 subjects	400 mg KD025 QD	4	2

KD025 will be supplied as 100 mg capsules or 200 mg tablets.

Product	Strength	Dosage Form	Route
KD025	100 mg	Yellow opaque capsule (size 00)	Oral
KD025	200 mg	Oblong yellow-coated tablet	Oral

Cohort 1: Subjects should take 2 capsules/1 tablet with their morning meal or within 5 minutes of finishing the meal.

Cohort 2: Subjects should take 2 capsules/1 tablet with their morning meal or within 5 minutes of completing the meal and 2 capsules with their evening meal or within 5 minutes of finishing the meal.

Cohort 3: Subjects should take 4 capsules/2 tablets with their morning meal or within 5 minutes of finishing the meal.

Subjects who have SD, PR, or CR at the time of decision to discontinue treatment and who come off study for reasons other than AEs will be tapered off KD025 by lowering the dose by 50% every 2 weeks until they reach a dose of 100 mg QD or equivalent. Further instructions will be listed in the pharmacy manual.

Subjects will be dispensed study drug to self-administer while on an outpatient basis and subjects will be provided a study drug diary in which to record the day and time of dosing. Subjects will return to the clinic as outlined in the Study Assessments table (Table 1), and will receive that day's dose of study drug (first dose for BID subjects) while at the clinic.

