14.7. Dispensing of Study Drug and Dosing Compliance

Subjects will be dispensed study drug to self-administer while on an outpatient basis. Subjects will return to the clinic as outlined in the Study Assessments (Table 1), and will receive that day's dose of study drug while at the clinic.

The amount of study drug dispensed to the subject at the beginning of each dosing month should be sufficient to allow for 1 month of dosing with KD025.

The investigator (or designee) will be responsible for recording this information on the appropriate study drug inventory. This inventory will be maintained throughout the duration of the trial and will be periodically reviewed by a representative of the sponsor.

The investigator (or designee) will instruct the subject that all dispensed bottles must be returned at each follow-up visit, at which time a capsule/tablet count will be conducted to assure subject dosing compliance.

Additionally, subjects will be required to keep study drug diaries in which they will record the date and time of study drug administrations. These diaries will be dispensed and/or reviewed/collected at each visit.

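### SAP 3.7 reports relative dose intensity as compliance, so a subject who takes every directed dose loses compliance after a hold with resumption, a dose reduction or the discontinuation taper

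*SAP*

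**What the plan says.** SAP 3.7 sets the measure: "The relative dose intensity (RDI) will be used to assess the treatment compliance". RDI is actual dose intensity over planned dose intensity, as a percentage. For the denominator, "The planned cumulative dose is the planned daily dose amount multiplied by the duration of exposure"; that duration runs from Study Day 1 to the date of last dose, inclusive. For the numerator, "The actual total daily dose will need the information of dose change and dose held (interruption) captured in CRF", on the Missed Dose and Dose Modification pages. Nothing resets the planned dose after a modification, and the taper is not mentioned.

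The protocol itself directs or permits lower dosing in several places:

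- Section 14.4 directs holds for certain toxicities, limits a pause to 14 days, and allows dosing to resume afterwards, in some cases at a reduced dose.
- Section 14.4.1 (Tables 5 and 6) permits one reduction.
- Section 14.1 has subjects with SD, PR or CR who stop for reasons other than AEs "tapered off KD025 by lowering the dose by 50% every 2 weeks until they reach a dose of 100 mg QD or equivalent".

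The protocol's own compliance checks are the diary and the count. Section 9.1 states: "Compliance with oral dosing will be confirmed using patient diaries, which will be examined at each visit". Under section 14.7, bottles come back at follow-up visits, "at which time a capsule/tablet count will be conducted to assure subject dosing compliance".

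**The concern.** Compliance should answer whether subjects took what they were told to take. Dose intensity answers how much drug they received relative to the starting plan. The two agree only while the prescribed dose stays at the cohort dose. Once it changes, RDI counts the instruction to take less in the same way as a missed dose.

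At stake is how the exposure and compliance table is read. In a dose-escalation study that also compares 200 mg BID with 400 mg QD, a low figure caused by toxicity management means something different from one caused by forgotten doses. As planned, one number carries both.

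**Working it through.** The documents state no RDI value or compliance threshold, so there is no figure to reproduce. The check applies the SAP formula to subjects who take every directed dose.

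**Inputs**

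- Planned daily dose, from Protocol 14.1: "Eligible subjects will receive KD025 200 mg QD, KD025 200 mg BID, or KD025 400 mg QD". That is 200 mg/day in Cohort 1 and 400 mg/day in Cohorts 2 and 3.
- Reduction, from Protocol Tables 5 and 6: half the planned daily dose in every cohort (Cohort 1 tablets reach it by alternate-day dosing).
- Hold, from Protocol 14.4: at most 14 days, the same for all cohorts.
- Taper, from Protocol 14.1: 200 to 100 mg in Cohort 1 (one step); 400 to 200 to 100 mg in Cohorts 2/3 (two steps).
- Assumed: time on full dose before any change, shown from 28 to 336 days; length of the 100 mg step, 14 days or not dosed at all; taper doses count towards the date of last dose, which is the literal reading.

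The duration cancels between the two intensities, so RDI = 100 × actual cumulative dose / (planned daily dose × days).

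**Reduction at Day 36, followed to Day 168** (35 full-dose days, 133 half-dose days)

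- Cohorts 2/3: (35×400 + 133×200) / (168×400) = 40,600 / 67,200 = 60.4%.
- Cohort 1: (35×200 + 133×100) / (168×200) = 20,300 / 33,600 = 60.4%.

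**14-day hold from Day 29, followed to Day 168** (same in every cohort)

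- Resume at full dose: (28 + 126) / 168 = 91.7%.
- Resume at half dose: (28 + 126×0.5) / 168 = 54.2%.
- Hold that ends in discontinuation: the window closes at the last dose before the hold, so 28 / 28 = 100%.

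**Taper after F full-dose days, 100 mg step given for 14 days**

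- Cohort 1: (F + 7) / (F + 14).
- Cohorts 2/3: (F + 7 + 3.5) / (F + 28).

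| F (days) | Cohort 1 | Cohorts 2/3 |
|---|---|---|
| 28 | 83.3% | 68.8% |
| 56 | 90.0% | 79.2% |
| 168 | 96.2% | 91.1% |
| 336 | 98.0% | 95.2% |

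If the 100 mg step is not dosed, Cohort 1 stays at 100%. Cohorts 2/3 become (F + 7) / (F + 14), which is 83.3% at 28 days and 98.0% at 336.

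**Real non-adherence mixed in.** Take 400 mg/day planned, a 14-day hold from Day 29, half dose to Day 168, and 10% of each prescribed dose missed.

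- Dose taken: 28×360 + 126×180 = 32,760 mg.
- Dose prescribed: 28×400 + 126×200 = 36,400 mg.
- Taken over prescribed: 90.0%. SAP RDI: 32,760 / 67,200 = 48.8%.

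**The case against.** RDI is a legitimate exposure summary, and the section is descriptive. Several stronger readings that a reader might draw are not supported by the documents.

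- *Subjects are classed as non-compliant.* SAP 3.7 sets no threshold and no category; it gives descriptive statistics only. The effect is a lower number, not a label.
- *The 400 mg/day cohorts are penalised throughout.* Reductions and holds cost the same proportion in every cohort. Of the mechanisms examined, only the taper depends on starting dose. It is the same for Cohorts 2 and 3, so it does not distort BID versus QD. A cohort-wide reduction (Protocol 14.2) could also separate the cohorts, because the same trigger in the 200 mg QD cohort ends the study (13.3). That depends on the trigger being met, and this point does not rely on it.
- *Toxicity and non-adherence cannot be told apart.* SAP Table 4 plans a separate table and listing of reductions and interruptions. Protocol 17.3.3 presents dose by visit and all alterations in administration. SAP 3.9.1 summarises TEAEs leading to dose modification. The gap is narrower: no missed-dose summary is listed, the taper is not named, and RDI is not split by cause.
- *The SAP ignores missed doses.* It does not; they enter the RDI numerator through the CRF.
- *Every modification is compulsory.* Resuming at a reduced dose is optional.

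These limits stand. They do not rescue RDI as the sole compliance figure, because the planned tables give no adherence rate once a dose has been modified.

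**Conclusion.** The point holds as one about a reported descriptive statistic. As written, SAP 3.7 gives a wrong compliance figure for any adherent subject who resumes after a hold, has a reduction or is tapered. The examples run from 98.0% down to 54.2% where 100% would be correct.

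The reduction and hold figures rest on the assumed timing and follow-up. The cohort contrast rests on the taper assumptions: with a 14-day 100 mg step the gap is 14.6 points after 28 full-dose days (83.33 − 68.75) and 2.8 after 336 (98.0 − 95.2). It arises only in tapered subjects. The length of that step is not stated in the protocol, which leaves further instructions to the pharmacy manual.

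No efficacy or safety result changes, since the mITT and Safety populations require only one dose. The change is still worth making, because the rule is explicit and a better one is available.

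**What to change.** In SAP 3.7:

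1. Describe RDI as an exposure measure only, and state whether taper days are inside or outside its window.
2. Define compliance (%) as 100 × total dose taken / total dose prescribed, summed by day. The prescribed dose is zero on directed hold days, the reduced dose after a reduction, and the step dose during the taper. An otherwise adherent subject then scores 100% in every cohort.
3. Take the data from the Missed Dose and Dose Modification CRF, with diary entries or capsule/tablet counts where these are in the database.
4. In SAP Table 4, add missed doses by cohort beside the existing reductions and interruptions table.

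The cost is SAP wording and one descriptive table. Two things need checking: whether the CRF records taper steps, and whether diary or count data can be analysed. Protocol 14.7 and 14.10.1 refer to an inventory and a dispensing log and do not say that counts are entered on the eCRF. The main calculation needs only the CRF that the SAP already names, provided the taper steps are recorded there.

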## **3.8 Endpoints for Activity Analysis**

### **3.8.1 Primary Endpoint**

The overall response rate (ORR) is the primary endpoint of the study.

The ORR is defined as the proportion of subjects meeting the overall response criteria assessment of CR or PR at any post-baseline response assessment.

The overall response determination of cGVHD is based on the cGVHD response assessment performed by clinicians as per the 2014 NIH Consensus Development Project for Clinical Trials in cGVHD criteria. The overall response is defined using the scores from 9 organs (skin, eyes, mouth, esophagus, upper GI, lower GI, liver, lungs, and joints and fascia; see [Appendix B](#)) plus global severity rating. The results of overall response at each assessment time point are evaluated by investigator and categorized as CR, PR, or Lack of Response (LR), where LR includes the response status of unchanged, mixed, or progression.

If a treated subject does not have any response assessment, this subject will be counted as a non-responder.

The ORR and its two-sided 95% CI using Clopper-Pearson method will be presented.

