	
The FFS will be defined as the time from first dose of study drug to either the start of another treatment, relapse of the underlying disease, or death. The time to FFS will be summarized for each treatment group.
 
The OS will be defined as the time from first dose of KD025 to the date of death due to any cause. Kaplan-Meier plots, descriptive statistics of OS and landmark OS at 6, 12, 18 and 24 months will be provided.
 
The TTNT will be defined as the time from the first dose of KD025 to the start of additional systemic cGVHD therapy.
 
Changes in corticosteroid and CNI dose will be evaluated and results will be summarized by treatment group. Corticosteroids may be tapered at the discretion of the investigator after 4 weeks of KD025 administration.
 
The DOR is defined as the time of initial response until documented progression. Responses by organ system (PR and CR) will be assessed based on the 2014 NIH Consensus Development Project on Clinical Trials in cGVHD.
 
The exploratory outcome variables are expression of several cytokines (including IL-17A, IL-21, and IL-2), and changes in percentages of immune-cell subtypes (including Th17 and Treg cells). Results will be summarized by treatment group.
 
Demographics, subject disposition, and screening and baseline characteristics will be summarized overall and by treatment group.
 
Treatment-emergent AEs will be evaluated using the CTCAE v4.03. The secondary safety outcome will be the number (%) of subjects experiencing AEs overall. The total sample size of 16 subjects per KD025 dose group will provide > 90% probability of one or more KD025 subjects experiencing an AE that has an underlying rate of $\geq 14\%$ and > 80% probability of one or more subjects in the study experiencing an AE that has an underlying rate of $\geq 10\%$.
 
Treatment-emergent AEs (TEAEs) will be summarized by treatment group using Medical Dictionary for Regulatory Activities (MedDRA[®]) System Organ Class (SOC) and preferred term (PT), classified from verbatim terms. MedDRA[®] Version 20.0 or higher will be used. The incidence and percentage of subjects with at least 1 occurrence of a preferred term will be included, according to the most severe grade using a 5-point scale (mild, moderate, severe, life threatening, or death). The number of events per preferred term will also be summarized. Causality (relationship to study treatment) will be summarized separately.
 
AEs, SAEs, treatment-related AEs, treatment-related SAEs, \geq Grade 3 AEs, treatment-related \geq Grade 3 AEs, and AEs leading to withdrawal or treatment discontinuation will be summarized overall and by treatment group according to SOC and PT. AEs will also be presented in listings. Duration of AEs will be determined and included in listings, along with

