17.4. Activity Analysis

The primary activity outcome will be the percentage of subjects who meet the OR criteria (PR + CR). This will be assessed overall (ie, any subject meeting the PR or CR criteria at any time point). For clarity, addition of new systemic therapy for cGVHD will be considered a KD025 treatment failure and will be considered progression of cGVHD for analysis purposes.

Secondary Endpoints

- Number and percentage of KD025 in subjects with steroid-dependent cGVHD who have a best response of PR or CR
- Change in cGVHD severity as based on the Physician-reported Global cGVHD Activity Assessment
- Change in symptom activity as based on cGVHD Activity Assessment Patient Self-Report
- Median FFS will be defined as the time from first dose of study drug to either the start of another treatment, relapse of the underlying disease, or death.
- Changes in corticosteroid and calcineurin inhibitor dose
- To evaluate DOR, which will be defined as the time of initial response until documented progression.
- To evaluate response by organ system. The response by organ system (PR and CR) will be assessed based on the 2014 NIH Consensus Development Project on Clinical Trials in cGVHD.
- Analyses of plasma PK of KD025 in subjects with cGVHD
- OS will be defined as the time from first dose of KD025 to the date of death due to any cause. Kaplan-Meier plots, descriptive statistics of OS and landmark OS at 6, 12, 18 and 24 months will be provided.
- TTNT will be defined as the defined as the time from the first dose of KD025 to the start of additional systemic cGVHD therapy Change in symptom burden/bother using the Lee cGVHD Symptom Scale.

Exploratory Endpoints

- Changes in the expression of several cytokines (including IL-17A, IL-21, and IL-2) in plasma after KD025 administration to subjects with cGVHD
- Changes in percentage of immune-cell subtypes (including Th17 and Treg cells) in whole blood after KD025 administration to subjects with cGVHD

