### **3.8.2 Secondary Endpoints**

#### **3.8.2.1 Duration of Response (DOR)**

The primary definition of DOR is the time from first documentation of response to the time of first documentation of deterioration from best response (e.g., CR to PR, or PR to LR).

The secondary definition of DOR is the time from first documentation of response to the time of first documentation of lack of response.

The tertiary definition of DOR is the time from first documentation of response to the time of initiation of new systemic cGVHD therapy (which will be defined by clinical team review).

The quaternary definition of DOR is the time from first documentation of response to the time of first documentation of lack of response (as the secondary definition) but with durations summed for multiple response/lack of response episodes.

The DOR will be reported only for responders and statistics will include:

- Kaplan-Meier plots and descriptive statistics of DOR. The censoring rules in [Table 2](#) will be applied
- Landmark analyses: Number and percentage of subjects with response sustained for  $\geq 12$ ,  $\geq 20$ ,  $\geq 24$ ,  $\geq 32$ ,  $\geq 36$ , and  $\geq 48$  weeks

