**Table 2. Censoring Rules for Duration of Response**

DOR	Events	Censoring
Primary	
 
• Deterioration from best response
 
• Initiation of new systemic therapy for cGVHD
 
• Death
 
	
 
• Last documented response assessment
 
• If LR or initiation of new systemic therapy happens immediately after two or more missed response assessments, the event date should be set as four weeks (one cycle) after last documented response assessment prior this event
 

Secondary	
 
• Documented LR
 
• Initiation of new systemic therapy for cGVHD
 
• Death
 
	
Tertiary	
 
• Initiation of new systemic therapy for cGVHD
 
• Death
 
	Last response assessment or long term follow up assessment, whichever is the latest and available
Quaternary	
 
• Documented LR
 
• Initiation of new systemic therapy for cGVHD
 
• Death
 
 
With summation of DOR from multiple episodes
	Same with censoring rule for primary and secondary

cGVHD = chronic graft versus host disease; DOR = duration of response; LR = lack of response

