### 3.8.2.2 Time-to-Response (TTR)

Time-to-response will be measured as the time from first treatment to the time of first documentation of response. Descriptive statistics and plots of cumulative number and percent of responders over time (at 4, 8, 12, 16, 24, 32, 40, and  $\geq 48$  weeks) will be provided. The TTR analyses will only be conducted for the Responder Population.

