### 3.8.2.4 Time to Next Therapy (TTNT)

The TTNT will be measured as the time from first treatment to the time of new systemic cGVHD treatment (which will be defined by clinical team review), censored by last response assessment or long term follow up assessment, whichever is the latest and available. TTNT will be analyzed by the Kaplan-Meier survival method as well as the landmark analysis at 6, 12, 18, and 24 months.

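### The SAP's ORR, Responder Population and time to response omit the protocol's treatment-failure rule for added systemic cGVHD therapy, so a first response after such therapy counts for KD025

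*SAP*

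**What the plan says.** **Protocol.** Section 17.4 defines the primary activity outcome as the percentage of subjects with PR or CR at any time point. The same paragraph, ahead of the secondary endpoints, adds that "addition of new systemic therapy for cGVHD will be considered a KD025 treatment failure and will be considered progression of cGVHD for analysis purposes". It gives no date after which a response is disregarded.

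**SAP, where the rule is absent.**
- Section 3.8.1: "The ORR is defined as the proportion of subjects meeting the overall response criteria assessment of CR or PR at any post-baseline response assessment". The category at each visit is the investigator's. The only explicit non-responder rule covers treated subjects with no response assessment.
- Section 3.2, Responder Population: "subjects in the mITT population that achieved a PR or CR response at any post-baseline response assessment".
- Section 3.8.2.2: "Time-to-response will be measured as the time from first treatment to the time of first documentation of response".

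**SAP, where the rule is present.**
- Table 2 lists "Initiation of new systemic therapy for cGVHD" as an event for all four DOR definitions.
- Section 3.8.2.4: "The TTNT will be measured as the time from first treatment to the time of new systemic cGVHD treatment".
- Section 3.8.2.7 makes the start of another systemic cGVHD treatment a failure event in FFS.

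**The concern.** The protocol's failure sentence stands beside the definition of response, yet the SAP applies it only to time-to-event endpoints. A subject whom the protocol calls a KD025 treatment failure can therefore be a KD025 responder in the primary analysis, on a response first seen under another therapy. Compared with a rule that stops crediting responses at new therapy, the literal SAP rule can only raise ORR.

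The same subject enters every analysis built on the Responder Population: time to response, DOR, the second organ-response denominator, and the corticosteroid and Lee Symptom Scale summaries by responder status. In DOR, the new-therapy event in Table 2 falls before time zero, and the SAP has no rule for that. Whoever programs the analysis would have to choose one, in an open-label study for which SAP 3.13 allows periodic interim analyses.

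**Working it through.** **1. The plan's own figures.** Protocol 17.2 assumes a 25% response rate and 16 subjects per group. Exact binomial tails give P(at least 3 of 16) = 0.803, against about 80% stated, and P(at least 2 of 16) = 0.937, against about 90% stated. The first is reproduced; the second is understated by 3.7 points. Neither depends on the present point. They supply the 25% used below.

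**2. Can the situation arise?** It needs systemic therapy added while KD025 continues, no earlier CR or PR, and a later response assessment.
- Response is assessed on Day 1 of each cycle from Cycle 2 and at EOT (Protocol 10.1).
- Subjects with a mixed response may stay on KD025 with medical monitor approval (Protocol 6.3 and 9.1).
- Starting new cGVHD therapy is not itself a listed reason to stop KD025 (Protocol 13.1.1), and Protocol 15 does not prohibit it. Exclusion criterion 11 is an entry criterion.
- Against this, disease progression and investigator decision are listed stop reasons. The 28-day follow-up visit is placed after the last dose and before any new therapy (Protocol 8.6; Table 1, footnote r).

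The route is open but narrow, mainly through mixed-response subjects kept on drug. No section describes add-on therapy and none bars it.

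**3. Effect on ORR.** Each such subject adds 1/16 = 6.25 points to a cohort, or 1/48 = 2.1 points overall. The documents give no count. Illustration from the planned 25%, with Clopper-Pearson 95% intervals as in SAP 3.8.1:

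| Extra subjects | Cohort of 16 | All 48 |
|---|---|---|
| 0 | 4/16 = 25.0% (7.3 to 52.4) | 12/48 = 25.0% (13.6 to 39.6) |
| 1 | 5/16 = 31.25% (11.0 to 58.7) | 13/48 = 27.1% (15.3 to 41.8) |
| 2 | not shown | 14/48 = 29.2% (17.0 to 44.1) |

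**4. Effect on DOR (constructed case).** Study day = (cycle − 1) × 28 + day. Therapy is added on C3D15, Day 71. First PR is on C4D1, Day 85. The last assessment is on C13D1, Day 337, with no death, no further new therapy and no later follow-up contact. The tertiary DOR is then:
- early event applied: 71 − 85 = −14 days;
- early event ignored: censored at 337 − 85 = 252 days = 36 weeks.

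SAP 3.8.2.1 also reports "Number and percentage of subjects with response sustained for" at least 12 to 48 weeks, including 36. Assume 5 responders in the cohort and 13 overall, each count including this subject, and half of the others sustained to 36 weeks:

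| Handling | Cohort | Overall |
|---|---|---|
| Early event applied | 2/5 = 40% | 6/13 = 46.2% |
| Early event ignored | 3/5 = 60% | 7/13 = 53.8% |
| Subject not a responder (the fix) | 2/4 = 50% | 6/12 = 50% |

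The fix moves this landmark by 10 points in the cohort and 3.8 points overall. The direction depends on the reading it replaces.

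**The case against.** **No stated rule is broken.** Protocol 17.4 keeps response at any time point, and SAP 3.8.1 follows it. The progression label does not settle the matter either: Protocol Appendix B also treats a mixed response as progression for analysis, and a later PR still counts. This stands. A reader might infer that the SAP violates a date cut in the protocol, but there is none. What remains is the treatment-failure wording, which Appendix B does not use for mixed response and which has no effect on ORR unless some response is disregarded.

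**The situation may never occur.** The follow-up rule expects new therapy after KD025 has ended. The protocol's definition of time to next treatment, "the time from the first dose of KD025 to the start of additional systemic cGVHD therapy", can mean subsequent therapy as easily as add-on therapy. Both points stand. A reader might see the KD025 taper in Protocol 9.1 as a second route, but the same follow-up rule speaks against therapy starting then.

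**The DOR distortion can be overstated.** A reader might infer that, once the early event is ignored, only death can end the tertiary DOR. Table 2 does not support that, since a further new therapy after the response is still an event. Nor is the gap between 40% and 60%, or between 46.2% and 53.8%, the effect of the fix; it separates two readings of the present SAP. The constructed case also needs 337 − 71 = 266 days of assessments after the added therapy.

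**Affected subjects would be visible.** The planned listings show response by visit, failure events and concomitant medications. That allows them to be found, but it does not say how they are counted.

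**Version lag is an unlikely explanation.** The SAP cites Amendment 6, and the Amendment 7 change log for Section 17.4 does not show the failure sentence as new.

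**Conclusion.** The point holds as a gap between protocol and SAP. The protocol places the treatment-failure sentence in the primary-outcome paragraph; the SAP carries it into DOR, TTNT and FFS but not into ORR, the Responder Population or time to response. This is more than missing detail, because the SAP's stated any-assessment rule gives a definite answer, and that answer credits KD025 with a response first seen under another therapy. It also leaves a DOR event before time zero without a rule.

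The size per subject is fixed at 6.25 points in a cohort and 2.1 points overall. The number of subjects is unknown and may be zero. The conclusion assumes that treatment failure is meant to bear on ORR, which is the natural reading of its position but not the only one. With an exploratory aim and no ORR threshold, no formal decision can be reversed. Severity is minor to moderate.

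**What to change.** In SAP 3.8.1 and 3.2, count as responders only subjects with a CR or PR assessed on or before the start of new systemic cGVHD therapy. Subjects who first respond later are non-responders. Subjects who responded earlier stay responders, in line with Table 2, where new therapy ends a response and does not erase it. Apply the same cut to best overall response, time to response and the start of DOR. State that it follows the treatment-failure wording of Protocol 17.4 and does not extend to documented progression without new therapy. Keep the any-time ORR as a sensitivity analysis.

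The start date is already needed for TTNT and FFS. The missing-day rule in SAP 3.1.5 should not be applied to this cut without review: it sets an undesired event to the first of the month. Therapy begun on the 20th with the day missing would be dated the 1st, and a genuine response on the 10th would be lost. When the day is missing and a response falls in the same month, settle the order in the clinical team review already planned for new systemic therapy, or report the result both ways.

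The cost is a sentence in each of the two sections and one date filter. ORR can only stay the same or fall slightly. A late KD025 response just after new therapy starts is not credited, and new therapy is treated more strictly than documented progression; the sensitivity analysis shows how much this matters. If the sponsor prefers the any-time reading, the SAP should say so and add a DOR rule for events before time zero.
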